## 7 STATISTICAL METHODOLOGY AND STATISTICAL ANALYSES

### 7.1 STATISTICAL METHODS

#### Summary statistics

For summary statistics described in this plan, the following values will be calculated, unless otherwise specified:

Number of cases, number of missing cases, mean, standard deviation, minimum, quartiles, and maximum

PFIZER CONFIDENTIAL

CT24-WI-GL03-RF03 2.0 *Non-Interventional Statistical Analysis Plan For Secondary Data Collection*  
Study 01-Jun-2020  
Page 16 of 30

**Number of digits**

The percentage (%) of frequency distribution will be rounded to one decimal place, unless otherwise specified, in the individual analysis items. Considering the summary statistics items (number of cases, number of missing cases, mean, standard deviation, minimum, quartiles, and maximum), mean, standard deviation, and quartiles will be rounded such that the decimal places are one digit lower than the original data.

## 7.2 STATISTICAL ANALYSES

### 7.2.1 Safety analyses

Not applicable

### 7.2.2 Analysis of primary, secondary, and CCI

#### Analysis of primary endpoints

##### 7.2.2.1 Demographic and clinical characteristics of patients

Source : FAS, Efficacy analysis set

population

Endpoints : Continuous variables

Age

Height

Body weight

BMI

CRP

eGFR

Number of metastatic organs

Number of risk factors

Observation duration (months)

#### Categorical variables

Age (2 categories)

Age (3 categories)

BMI (3 categories)

Gender

CRP (3 categories)

eGFR (3 categories)

Smoking history

ECOG Performance Status

ECOG Performance Status ①

ECOG Performance Status ②

Invasion depth (T factor)

Lymph node metastasis (N factor)

Distant metastasis (M factor)

Tumor histological type

Presence or absence of sarcomatoid component

PFIZER CONFIDENTIAL

CT24-WI-GL03-RF03 2.0 *Non-Interventional Statistical Analysis Plan For Secondary Data Collection*

Study 01-Jun-2020

Page 17 of 30

Fuhrman grade  
 Fuhrman grade (3 categories)  
 Proteinuria  
 Performance of nephrectomy  
 Presence or absence of metastasis  
     Metastatic site  
     Metastatic site: Lung  
     Metastatic site: Liver  
     Metastatic site: Bone  
     Metastatic site: Brain  
     Metastatic site: Regional lymph node  
     Metastatic site: Distant lymph node  
     Metastatic site: Other  
 Number of metastatic organs (5 categories)  
 Presence or absence of clinically important comorbidities  
 Presence or absence of clinically important concomitant drugs  
 Less than 1 year from diagnosis to the initiation of systemic therapy  
 Karnofsky Performance Status <80%  
 Hemoglobin value below the lower normal limit  
 Corrected calcium value above the upper normal limit  
 Neutrophil count above the upper normal limit  
 Platelet count above the upper normal limit  
 IMDC risk group  
 Number of risk factors (7 categories)  
 Breakdown of IMDC risk factors by the number of risk factors

**Analysis content :**

The following aggregation will be performed for endpoints:  
 Summary statistics will be calculated for continuous variables.  
 A frequency table (number of cases, percentage (%)) will be created for categorical variables.  
 A frequency table (number of cases, percentage (%)) will also be created for details regarding clinically important comorbidities and concomitant drugs

【Division of categorical variables】

Factor	Category
Age (2 categories)	<75 years; ≥75 years
Age (3 categories)	<65 years; ≥65 years and <75 years; ≥75 years
Gender	Male; Female
Body mass index (3 categories)	<25 kg/m  ; ≥25 kg/m  ; Unknown
C-reactive protein (3 categories)	<5 mg/L; ≥5 mg/L; Unknown
Estimated glomerular filtration rate (3 categories )	<60; ≥60; Unknown
Smoking history	No (no past smoking); No (history of past smoking); Yes; Unknown

PFIZER CONFIDENTIAL

ECOG Performance Status	0; 1; 2; 3; 4
ECOG Performance Status ①	0; 1; ≥2
ECOG Performance Status ②	0 or 1; ≥2
Invasion depth (T factor)	TX; T0; T1; T1a; T1b; T2; T2a; T2b; T3; T3a; T3b; T3c; T4; Unknown
Lymph node metastasis (N factor)	NX; N0; N1; Unknown
Distant metastasis (M factor)	MX; M0; M1; Unknown
Tumor histological type	Clear cell renal cell carcinoma; Papillary renal cell carcinoma; Chromophobe renal cell carcinoma; Other
Presence or absence of sarcomatoid component	No; Yes
Fuhrman grade	Grade 1; Grade 2; Grade 3; Grade 4; Unknown
Fuhrman grade (3 categories)	Grade 1 or Grade 2; Grade 3 or Grade 4; Unknown
Proteinuria	–; ±; 1+; 2+; 3+; Not measured
Performance of nephrectomy	No; Yes; Unknown
Presence or absence of metastasis	No; Yes; Unknown
Metastatic site	Lung; Liver; Bone; Brain; Regional lymph node; Distant lymph node; Other
Metastatic site: Lung	No; Yes; Unknown
Metastatic site: Liver	No; Yes; Unknown
Metastatic site: Bone	No; Yes; Unknown
Metastatic site: Brain	No; Yes; Unknown
Metastatic site: Regional lymph node	No; Yes; Unknown
Metastatic site: Distant lymph node	No; Yes; Unknown
Metastatic site: Other	No; Yes; Unknown
Number of metastatic organs	0; 1; 2; 3; ≥4
Presence or absence of clinically important comorbidities	No; Yes; Unknown
Presence or absence of clinically important concomitant drugs	No; Yes; Unknown
Less than 1 year from diagnosis to the initiation of systemic therapy	Yes; No
Karnofsky Performance Status <80%	Yes; No
Hemoglobin value below the lower normal limit	Yes; No
Corrected calcium value above the upper normal limit	Yes; No

PFIZER CONFIDENTIAL

CT24-WI-GL03-RF03 2.0 *Non-Interventional Statistical Analysis Plan For Secondary Data Collection*  
 Study 01-Jun-2020  
 Page 19 of 30

Neutrophil count above the upper normal limit	Yes; No
Platelet count above the upper normal limit	Yes; No
IMDC risk group	Low risk; Medium risk; High risk
Number of risk factors (7 categories)	0; 1; 2; 3; 4; 5; 6

### **Analysis of secondary objectives**

#### **7.2.2.2 Real-world progression-free survival**

Source : Efficacy analysis set  
 population  
 Endpoint : Real-world PFS  
 Analysis content : For the endpoint, the median and its 95% confidence interval will be calculated using the Kaplan–Meier method. In addition, the Kaplan–Meier curve will be plotted, and the PFS rate for every 12 months and its 95% confidence interval will be calculated. Greenwood’s formula will be used to calculate the confidence interval for the PFS rate. In addition, the number of event-onset cases and the number of censored cases will be presented. A frequency table (number of cases, percentage (%)) will be created, considering the reasons for the event and reasons for censoring. In order to evaluate the observation period, the median observation period and its 95% confidence interval will be calculated by estimating the reverse Kaplan-Meier curve in which censoring patients are regarded as patients with events and patients with events are regarded as censoring patients.

#### **【Division of categorical variables】**

Factor	Category
Reasons for the event	Disease progression after the start of avelumab plus axitinib; Death
Reasons for the censoring	No disease progression during or after first-line therapy; second-line therapy started; nephrectomy performed

#### **7.2.2.3 Overall survival (OS)**

Source : Efficacy analysis set  
 population  
 Endpoint : OS  
 Analysis content : For the endpoint, the median and its 95% confidence interval will be calculated using the Kaplan–Meier method. In addition, the Kaplan–Meier curve will be plotted, and the survival rate for every 12 months

PFIZER CONFIDENTIAL

and its 95% confidence interval will be calculated. Greenwood's formula will be used to calculate the confidence interval for the survival rate.

In addition, a frequency table (number of cases, percentage (%)) will be created, considering the event onset, censoring, reasons for the event, and reasons for censoring.

In order to evaluate the observation period, the median observation period and its 95% confidence interval will be calculated by estimating the reverse Kaplan-Meier curve in which censoring patients are regarded as patients with events and patients with events are regarded as censoring patients.

#### 【Division of categorical variables】

Factor	Category
Reasons for the event (cause of death)	Death from primary disease; Death related to avelumab plus axitinib combination therapy; Death not related to avelumab plus axitinib combination therapy
Reasons for censoring	Survival; Untraceable

#### 7.2.2.4 Objective response rate (ORR)

Source : Efficacy analysis set population  
 Endpoints : ORR  
 Presence or absence of confirmation of BOR to treatment  
 Evaluation method  
 Determination of BOR (tumor assessment)  
 Analysis content : The number of target cases, number of objective responding cases, and objective response rate and its 95% confidence interval will be calculated to establish the ORR of the endpoint.  
 In addition, the Clopper-Pearson method will be used to calculate the confidence interval.  
 In addition, a frequency table (number of cases, percentage (%)) will also be created, considering the achievement of BOR to treatment, evaluation method, and determination of BOR (tumor assessment).

#### 【Division of categorical variables】

Factor	Category
Objective response to avelumab plus axitinib combination therapy	Objective response
Achievement of the best overall response to treatment	No; Yes
Evaluation method	RECIST; Other than RECIST

PFIZER CONFIDENTIAL

Determination of best overall response (tumor assessment)	CR; PR; SD; PD; NE
---	--------------------

CR, complete response; PR, partial response; PD, progressive disease; NE, not evaluable for response.

#### 7.2.2.5 Best overall response for primary lesions

Source : Efficacy analysis set  
 population  
 Endpoints : ORR  
     Presence or absence of confirmation of BOR to treatment  
     Evaluation method  
     Determination of BOR (tumor assessment)  
 Analysis content : The number of target cases, number of objective responding cases, and objective response rate and its 95% confidence interval will be calculated to establish the ORR of the endpoint.  
     In addition, the Clopper–Pearson method will be used to calculate the confidence interval.  
     A frequency table (number of cases, percentage (%)) will also be created, considering the achievement of BOR to treatment, evaluation method, and determination of BOR (tumor assessment).

#### 【Division of categorical variables】

Factor	Category
Objective response of primary lesions	Objective response
Achievement of best overall response to treatment	No; Yes
Evaluation method	RECIST; Other than RECIST
Determination of best overall response (tumor assessment)	CR; PR; SD; PD; NE

CR, complete response; PR, partial response; PD, progressive disease; NE, not evaluable for response.

#### 7.2.2.6 Time to treatment discontinuation (TTD) of avelumab plus axitinib combination therapy as first-line therapy

Source : Efficacy analysis set  
 population  
 Endpoints : TTD of avelumab plus axitinib combination therapy as first-line therapy  
     TTD of avelumab as first-line therapy  
     TTD of axitinib as first-line therapy  
 Analysis content : Considering the endpoints, the median and its 95% confidence interval will be calculated using the Kaplan–Meier method. In addition, the Kaplan–Meier curve will be plotted, and the survival

PFIZER CONFIDENTIAL

rate for every 3 months, along with its 95% confidence interval, will be calculated. Greenwood's formula will be used to calculate the confidence interval for the survival rate.

In addition, a frequency table (number of cases, percentage (%)) will be created, considering the event onset, censoring, reasons for the event, and reasons for censoring.

**【Division of categorical variables】**

Factor	Category
Reasons for the event	Disease progression/adverse event/other (death)/other (excluding death)
Reasons for the censoring	Treatment ongoing; Discontinuation due to efficacy

**7.2.2.7 Treatment patterns for avelumab plus axitinib combination therapy as first-line therapy in a real-world setting**

Source : FAS, Efficacy analysis set

population

Endpoints : Continuous variables

Duration of treatment for avelumab plus axitinib (days)

Duration of treatment for avelumab (days)

Duration of treatment for axitinib (days)

Initial dose of avelumab [daily dose (mg)]

Initial dose of axitinib [daily dose (mg)]

Avelumab dose intensity (DI)

Axitinib DI

Axitinib relative DI (RDI)

Categorical variables

Initial dose of avelumab [daily dose (mg)]

Initial dose of axitinib [daily dose (mg)]

Presence or absence of changes in the avelumab dose

Presence or absence of changes in the avelumab dose (dose reduction)

Reason for changes in the avelumab dose (dose reduction)

Presence or absence of change in the avelumab dose (dose increase)

Termination of avelumab administration

Reason for termination of avelumab administration

Presence or absence of changes in the axitinib dose

Presence or absence of changes in the axitinib dose (dose reduction)

Reason for change in the dose of axitinib (dose reduction)

Presence or absence of changes in the axitinib dose (dose increase)

Termination of axitinib administration

PFIZER CONFIDENTIAL

## Reason for termination of axitinib administration

## Notes:

- 1) 10 mg/day is set as the criterion.
- 2) Dose changes will be aggregated based on the input items, considering the administration status in the case report form. The criteria for dose changes will be determined based on the record of the immediately preceding administration for both avelumab and axitinib.
- 3) Considering the reason for dose reduction, if the same reason is documented in multiple records of the case, each reason will be counted as one case.

**Analysis content :** The following aggregation will be performed for the endpoints:  
 Summary statistics will be calculated for continuous variables.  
 A frequency table (number of cases, percentage (%)) will be created for categorical variables.  
 In addition, a list presenting the reasons underlying the changes in the avelumab dose (dose increase) and those underlying changes in the axitinib dose (dose increase) will be created.  
 Furthermore, a swimmer plot with the date of initiation as the avelumab + axitinib administration start date (earlier date if they are different) will be created.

## 【Division of categorical variables】

Factor	Category
Initial avelumab dose [daily dose (mg)]	<10 mg/kg; 10 mg/kg; >10 mg/kg
Initial axitinib dose [daily dose (mg)]	<2 mg; ≥2 mg and <5 mg; ≥5 mg and <10 mg; <10 mg; 10 mg; >10 mg
Presence or absence of changes in the avelumab dose	No; Yes
Presence or absence of changes in the avelumab dose (dose reduction)	No; Yes
Reason for changes in the avelumab dose (dose reduction)	Disease progression; Adverse event; discontinuation due to efficacy ; Other
Presence or absence of changes in the avelumab dose (dose increase)	No; Yes
Termination of avelumab administration	No; Yes
Reason for termination of avelumab administration	Disease progression; Adverse event; discontinuation due to efficacy ; Other
Presence or absence of changes in the axitinib dose	No; Yes

PFIZER CONFIDENTIAL

Presence or absence of changes in the axitinib dose (dose reduction)	No; Yes
Reason for changes in the axitinib dose (dose reduction)	Disease progression; Adverse event; discontinuation due to efficacy ; Other
Presence or absence of changes in the axitinib dose (dose increase)	No; Yes
Termination of axitinib administration	No; Yes
Reason for termination of axitinib administration	Disease progression; Adverse event; discontinuation due to efficacy ; Other

#### 7.2.2.8 Clinical use of corticosteroids for immune-related adverse events (irAEs) occurring during the course of avelumab plus axitinib combination therapy

Source : FAS, Efficacy analysis set

population

Endpoints : Continuous variable

Duration of treatment for corticosteroids (days)

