9.2. Setting

This retrospective chart review will evaluate patient data derived from patient's existing medical records from the enrolled patients. All decisions regarding the clinical management and treatment of the patients are made by the investigator as part of standard care in a real-world setting and are not contingent upon the patient's participation in the study. Data will be collected at each study site (if available).

PFIZER CONFIDENTIAL

CT24-WI-GL02-RF02 4.0 Non-Interventional Study Protocol Template For Secondary Data Collection Study 01-Jun-2022

The study period is from 20 December 2019 to 31 October 2022. Patients with index date between 20 December 2019 and 17 October 2022 will be enrolled in this study. To ensure a 2 weeks follow up period, patients with an index date between 20 December 2019 and 17 October 2022 will be included in this study. The period of 2 weeks is determined based on the dosing interval for avelumab, in consideration of the fact that the start times of administration for avelumab and axitinib may differ.

- Index date: The date of first prescription of avelumab plus axitinib combination therapy.
- Observation period: Patients will be followed from the index date to 31 October 2022.

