9.7.1. Analysis Population

Full analysis set (FAS): The FAS will consist of patients who meet the inclusion criteria and do not meet the exclusion criteria.

Efficacy analysis set: The efficacy analysis set is a subset of the FAS that includes patients whose index date is prior to 30 April 2022 to ensure a 6-months follow-up period.

Subgroups: A subgroup analysis will be considered, including but not limited to subgroups categorized by IMDC risk group, age (≥ 75 years or < 75 years), and the presence or absence of corticosteroid administrations for irAE in the medical record.

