## **5 ENDPOINTS AND COVARIATES**

#### Handling of data on the number of days

The number of days from the start date to the target date will be calculated as follows:

- The target date is earlier than the start date = Target date — Start date
- The target date is on or after the start date = Target date — Start date + 1

The number of days will be handled as follows:

- ✓ 1 week = 7 days
- ✓ 1 month = 30.4375 days
- ✓ 1 year = 365.25 days

In addition, missing data will be imputed with reference to "6. HANDLING OF MISSING VALUES."

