##### Categorical variables

Administration of corticosteroid therapy for irAEs

Administration of high-dose corticosteroid therapy for irAEs (prednisolone-equivalent of  $\geq 40$  mg)

Analysis content : The following aggregation will be performed for the endpoints:  
Summary statistics will be calculated for continuous variables.  
A frequency table (number of cases, percentage (%)) will be created for categorical variables.  
In addition, a frequency table (number of cases, percentage (%)) will also be created for the details of other drugs.

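### Adverse-event stopping and steroid use for irAEs are reported only as crude percentages over very unequal follow-up, so neither can be read as the risk at any stated time

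*SAP*

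**What the plan says.** Protocol 9.2 fixes the follow-up. On entry it states: "To ensure a 2 weeks follow up period, patients with an index date between 20 December 2019 and 17 October 2022 will be included". On the end of observation: "Observation period: Patients will be followed from the index date to 31 October 2022". The efficacy analysis set (Protocol 9.7.1, repeated in SAP 4.3) is restricted to "patients whose index date is prior to 30 April 2022 to ensure a 6-months follow-up period".

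Three places in the SAP bear on the two outcomes:

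- **7.2.2.8, steroids for irAEs.** The population line is "Source : FAS, Efficacy analysis set". Any use and high-dose use are categorical, and the method is "A frequency table (number of cases, percentage (%)) will be created for categorical variables".
- **7.2.2.7, treatment patterns.** The populations and method are the same. "Reason for termination of avelumab administration" is one row, with a matching row for axitinib, and adverse event is one of its categories. The section does not say whether the percentage is of all patients or of those who stopped.
- **7.2.2.6, TTD.** Stopping for any reason other than efficacy is estimated by Kaplan-Meier in the efficacy set, for the combination and for each drug, with a survival "rate for every 3 months, along with its 95% confidence interval, will be calculated". Adverse event is one of four event reasons, tabulated by frequency.

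Some context on time is planned: observation duration in the baseline table (7.2.2.1), and treatment durations and a swimmer plot (7.2.2.7).

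**The concern.** Whether a patient has received steroids for an irAE, or has stopped because of an adverse event, depends on how long that patient was at risk. A patient indexed on 17 October 2022 with no steroid use by the end of the month is a No, with the same weight as a No observed for almost three years. A crude percentage averages over such patients. Its value depends on when sites began using the regimen as well as on the regimen itself.

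The SAP handles this for stopping overall, by censoring in Kaplan-Meier, but the visible text does not carry it through to stopping because of an adverse event or to steroid use. Since SAP 5.2 and 7.2.1 plan no safety endpoints or safety analyses, readers are likely to take tolerability from these tables. Someone who quotes the percentage will attach a time to it, and the plan supplies none.

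**Working it through.** **1. Follow-up range from the plan's dates.** Inputs: index dates from 20 December 2019 to 17 October 2022; efficacy set up to 29 April 2022; cut-off 31 October 2022. SAP section 5 counts target minus start plus 1 day, with "1 month = 30.4375 days".

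| Set | Shortest | Longest |
|---|---|---|
| FAS | 14 days elapsed (15 by the rule; 15/30.4375 = 0.49 months) | 1,046 days elapsed (1,047 by the rule; 34.4 months) |
| Efficacy set | 185 days elapsed (186 by the rule; 6.11 months) | as FAS |

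The stated minimum of 2 weeks is reproduced, and so is the 6-month minimum. This is potential follow-up; death or a last visit can shorten it.

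**2. Spread under uniform accrual (assumed).** Share of the FAS with under 12 months: (12 − 0.49)/(34.40 − 0.49) = 34%. Under 24 months: 69%. In the efficacy set: (12 − 6.11)/(34.40 − 6.11) = 21%, and 63%.

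**3. Crude percentage against risk at a fixed time.** The documents give no event rates, so these are assumptions: constant hazards, median time to any stop of 12 months, and a share q = 0.30 of stops due to an adverse event.

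λ = ln 2/12 = 0.05776 per month; F(t) = q(1 − e^(−λt)).

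- F(6) = 0.30 × (1 − 0.7071) = 8.8%
- F(12) = 0.30 × 0.50 = 15.0%
- F(24) = 0.30 × 0.75 = 22.5%

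With follow-up uniform on (a, b), the crude percentage is the mean of F over that range: q[1 − (e^(−λa) − e^(−λb))/(λ(b − a))].

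- FAS: 0.30 × [1 − (0.9719 − 0.1371)/(0.05776 × 33.91)] = 0.30 × 0.574 = 17.2%
- Efficacy set: 0.30 × [1 − (0.7026 − 0.1371)/(0.05776 × 28.29)] = 0.30 × 0.654 = 19.6%

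Both crude figures lie between the 12- and 24-month risks.

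**4. Range of assumptions.** For medians of 8 to 18 months and shares of 20% to 40%, the crude figure is below the 24-month risk by 21–25% (relative) in the FAS and 11–14% in the efficacy set. In every combination the FAS figure exceeds the 12-month risk.

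**5. A second model, with accrual and hazard shape varied.** Assume a 12-month risk of 20% and a competing hazard of ln 2/13.8 per month. The 13.8 months is the median PFS of the combination arm in the Phase 3 trial cited in Protocol section 7, used only to set a plausible scale. The risk is then 12.2% at 6 months and 28.1% at 24 months under constant hazard.

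| Accrual and hazard | Crude FAS | 12-month risk | 24-month risk |
|---|---|---|---|
| Uniform, constant | 21.9% | 20.0% | 28.1% |
| Uniform, hazard falls to one fifth after 6 months | 19.8% | 20.0% | 22.7% |
| Skewed to recent dates, constant | 17.4% | 20.0% | 28.1% |
| Skewed to early dates, constant | 26.4% | 20.0% | 28.1% |

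For the same underlying risk, the accrual pattern alone moves the crude figure from 17.4% to 26.4%, on either side of the 12-month value.

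**6. The unstated denominator.** In the model of step 3, adverse-event stops are 17.2% of all FAS patients. Any stop has occurred in 57.4%, so among those who stopped the figure is 17.2/57.4 = 30%. Both could appear in the same row under the current wording.

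**The case against.** The strongest reply is that these are utilisation tables. The objectives are to describe steroid use and treatment patterns, no hypothesis is tested, and the proportion treated in the observed cohort answers that question directly. If reason for termination is a percentage of those who stopped, it is a distribution of reasons and not a risk. The context on time is also real: observation duration, treatment durations, 3-monthly TTD rates and the swimmer plot. This stands as a reason to keep the frequency tables, and it limits the weight of the point. It does not supply an estimate of stopping because of an adverse event, or of steroid use, at any stated time.

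A reader might go further and infer that the crude percentages understate the risk. The documents do not support that. The shortfall appears against a long horizon such as 24 months, which the plan does not name for these items. Against 6 months the crude figure is too high under uniform accrual, and against 12 months it can fall either way. The largest shortfalls also belong to the FAS alone, while every one of these tables is produced in the efficacy set too.

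A reader might also infer that comparison across the three studies of the series is damaged. Protocol section 7 describes different follow-up periods, but no visible text plans to compare these percentages across studies.

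Finally, parts of the SAP between 5.2 and 5.4 and after 7.2.2.10 are blacked out, so the absence of a time-based analysis can be asserted only for the visible text.

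**Conclusion.** The point holds as a matter of interpretability. In the visible SAP, adverse-event-related stopping and steroid use for irAEs are crude percentages over potential follow-up of 2 weeks to 34 months (FAS) or 6 to 34 months (efficacy set). They refer to no time point, and the denominator for reason of termination is open.

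The follow-up range comes from the plan's own dates. The size of the discrepancy rests on assumed accrual, hazards and adverse-event share. In the main illustration the crude FAS figure is 2.2 points above the 12-month risk (17.2 − 15.0) and 5.3 points below the 24-month risk (22.5 − 17.2). A general claim of understatement does not follow. For a descriptive study this is a worthwhile, inexpensive improvement and does not invalidate the plan.

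**What to change.** Keep the frequency tables. In 7.2.2.7, state whether reason for termination is a percentage of all patients or of those who stopped. In 7.2.2.7 and 7.2.2.8, show median follow-up beside the percentages.

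Add Aalen-Johansen cumulative incidence with 95% confidence intervals for termination because of an adverse event, separately for the combination, avelumab and axitinib. Use the TTD population (efficacy set, optionally also the FAS) and the existing 3-month steps. Other stopping reasons and death are competing events. State how discontinuation due to efficacy is handled: keeping it censored matches the TTD definition, while treating it as a competing event reflects that such a patient can no longer stop for toxicity.

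For first steroid use for an irAE, do the same only if the start date is in the eCRF. Protocol Table 1 lists drug and dose; the steroid duration in 7.2.2.8 implies dates but does not list a start date. Death is the competing event. End of treatment should not be one, because steroids begun after stopping for an irAE that arose on treatment would be lost. Without a start date, the crude percentage with median follow-up is the most that can be reported.

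The cost is SAP wording and modest programming, since SAP 5.1 already derives the end dates and reasons for TTD. Late intervals will be wide: with about 150 patients and uniform accrual, roughly 46 (150 × 0.31) have 24 months of potential follow-up, before deaths and losses. If the redacted sections already contain such estimates, a cross-reference is enough for that part.
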